**Evaluation of the effect of a nasal allergen challenge with  
Dermatophagoides farinae extract on nasal airway  
inflammation in allergic individuals, comparing e-cigarette  
users to cigarette smokers and non-smokers**

**NCT number** NCT03023397  
**Document Date** 02/20/2017

**6.1. Protocol 1: Evaluation of the effect of a nasal allergen challenge with *Dermatophagoides farinae* extract on nasal airway inflammation in allergic individuals, comparing e-cigarette users to cigarette smokers and non-smokers.**

**a. Objectives and Purpose.** The purpose of this pilot study is to evaluate allergen-induced inflammation in nasal lavage samples following *Dermatophagoides farinae* intranasal challenge in e-cigarette users, cigarette smokers, and non-smokers.

**b. Patient inclusion and exclusion criteria.**

We will recruit allergic subjects with or without mild asthma, ages 18-50 years, including 15 e-cigarette users, 15 tobacco cigarette smokers, and 15 non-smokers (classification described below). There will be no gender or ethnic restrictions. Allergy skin testing to *D. farinae* will be performed to confirm the presence of allergic sensitization. Only individuals sensitive to house dust mite will be selected for participation. Spirometry will be performed to determine the current level of lung function. Those with an FEV1 (forced expiratory volume in the first second) of at least 80% predicted for age, gender, race, and height and an FEV1 to FVC (forced vital capacity) ratio of at least .75 will be eligible for the study. Subjects for this study will be both mild asthmatic and non-asthmatic healthy volunteers, ages 18-50 years and to include both males and females. Our recruitment goal includes 45 volunteers with at least 50% female subjects and at least a 30% minority representation. It is anticipated that the demographics of our patient population will reflect those of the local university community. Many determinations (e.g. spirometry, allergy skin testing) are made as a part of a separate screening protocol, IRB #98-0799, which is performed to identify subjects for potential participation in experimental challenge protocols such as this one.

Inclusion criteria

1. Specific allergy to house dust mite *D. farinae* confirmed by positive immediate skin test response.
2. Subjects may be enrolled with mild asthma if an FEV1 of at least 80% of predicted and FEV1/FVC ratio of at least .75 (without use of bronchodilator medications for 12 hours), consistent with lung function of persons with mild episodic or mild persistent asthma is demonstrated. For the purpose of this protocol, an asthmatic individual will be defined as having a) positive methacholine challenge with a provocative concentration of methacholine producing a 20% fall in FEV1 (PC20 methacholine) with less than or equal to 10 mg/ml; OR b) physician diagnosed asthma with symptoms and chronic daily therapy consistent with the mild asthma.
3. Subjects will be classified as tobacco smokers, e-cigarette users, or non-smokers according to the following guidelines:

	Tobacco Smokers	E-cigarette Users	Non-smokers
Average cigs/wk	>35 cigs/week	<7 cigs/week	none
Average vapor puffs/day	<18 puffs/day	≥18 puffs/day	none
Hookah use	<30 minutes/week	<30 minutes/week	<30 minutes/week
Duration of use	If former heavy e-cig user, must be <18 puffs/day for ≥6 months	E-cig user ≥6 months; if former heavy tobacco user, must be <7 cigs/week for ≥6 months	Must be abstinent from tobacco or e-cig products for ≥6 months

4. Ability to withhold antihistamine medications for one week prior to baseline and allergen challenge visits.
5. Subjects must be able and willing to give informed consent.

#### Exclusion criteria

1. Any chronic medical condition considered by the PI as a contraindication to the allergen challenge study including significant cardiovascular disease, diabetes requiring medication, chronic renal disease, bleeding disorder, or chronic thyroid disease.
2. Physician directed emergency treatment for an asthma exacerbation within the preceding 12 months.
3. Use of systemic steroid therapy within the preceding 12 months for treatment of an asthma exacerbation.
4. Use of inhaled or nasal steroids, cromolyn or leukotriene receptor antagonists (Montelukast or Zafirkulast) within the past month (except for use of cromolyn exclusively prior to exercise).
5. Subjects who smoke marijuana or use illicit drugs will be excluded.
6. Use of daily theophylline within the past month.
7. Use of nasal medications that might alter the response to nasal allergen challenge including anti-inflammatory and anti-histamine agents within one week of challenge.

8. Inability to withhold inhaled or oral bronchodilator medications for 12 hours prior to allergen challenge.
9. Pregnancy or nursing a baby.
10. Women of child-bearing age who are not using dependable contraception (such as birth control pills, IUD, estrogen patches) or who are not completely abstinent.
11. Nighttime symptoms of cough or wheeze greater than 1x/week at baseline (not during a clearly recognized viral induced asthma exacerbation) which would be characteristic of a person of moderate or severe persistent asthma as outlined in the current NHLBI guidelines for diagnosis and management of asthma.
12. Exacerbation of asthma more than 2x/week which would be characteristic of a person with moderate or severe persistent asthma as outlined in the current NHLBI guidelines for diagnosis and management of asthma.
13. Daily requirement for albuterol due to asthma symptoms (cough, wheeze, chest tightness) which would be characteristic of a person of moderate or severe persistent asthma as outlined in the current NHLBI guidelines for diagnosis and management of asthma. (Not to include prophylactic use of albuterol prior to exercise).
14. Viral upper respiratory tract infection or other acute inflammatory conditions of the nose or paranasal sinuses, such as sinusitis, within 4 weeks of challenge.
15. Any acute infection requiring antibiotics within 4 weeks of challenge.
16. Participating in an allergen inhalation study within 2 weeks of this challenge or use of any *other* investigational agent within the last 30 days.
17. Use of tricyclic antidepressants or beta-blockers.
18. Use of MAO inhibitors or any medications known to interfere with the treatment of anaphylaxis.
19. Subjects with a history of immunologic disease or undergoing immune suppression for cancer or other diseases.

**c. Design of Study.**

This study is designed to evaluate the effect of nasally applied *D. farinae* allergen extract on changes in nasal lavage, peripheral blood, and nasal epithelial cells in e-cigarette users compared to cigarette smokers and non-smokers. The principal endpoint is  $\Delta$ eosinophils/mL of nasal lavage fluid. Nasal allergen will be administered in a graded fashion distributing the dose equally between both nares with 100, 500 and 1,000 AU of *Der f* allergen extract delivered via nasal meter-dosed pump. Single-use nasal metered-dose pumps will be purchased from Professional Compounding Center of America, Houston, TX.

Secondary and exploratory endpoints will include nasal fluid cytokines, chemokines, markers of cellular activation, and mRNA from peripheral blood cells and nasal epithelial cells to examine gene expression profiles before and after nasal allergen challenge.

#### **d. Dosage**

*Dermatophagoides farinae* (*Der f*) allergen extract dilutions will be prepared in sterile saline by the University of North Carolina Hospitals Investigational Drug Service. It will be administered from a handheld nasal metered dose sprayer. The maximum cumulative dose that will be administered is 1600 AU of *D. farinae* extract distributed equally between both nares. Symptoms will be monitored and scored at regular intervals following allergen challenge. The challenge protocol is outlined in section “e” below.

#### **e. Observations and Measurements**

##### **Observation Schedule:**

Prior to any nasal inhalation challenge, subjects will undergo a physical examination of the ears, nose, throat (noting the uvula) and chest and will have an assessment of vital signs (temperature, pulse, respiratory rate, blood pressure), Total Nasal Symptom Score (TNSS) assessment and undergo spirometry to rule out acute illness prior to challenge. All female volunteers will undergo a urine pregnancy test. After adequate lung function has been documented, nasal allergen challenge will take place as outlined above. A physician will be immediately available during the challenge.

After nasal allergen challenge is complete, the subjects will be observed in CEMALB until venipuncture, nasal lavage (NL), epithelial lining fluid (ELF), and nasal epithelial cell (NEC) sampling are complete. Subjects will not be discharged from the CEMALB unit following challenge until FEV1 is within 90% of baseline values or higher. A physician will be on call following the challenge session for telephone consultation with the volunteer subject at any time following the nasal challenge.

Each subject will have four study visits:

##### **Visit 0: Screening allergen challenge day studies:**

1. Consent obtained
2. Urine pregnancy test for females of child bearing potential

3. Vital signs
4. Medical history (including medications) and physical exam (including oral exam, noting the uvula), and a smoking use questionnaire will be obtained.
5. Skin testing for *D farinae* sensitization (unless previously obtained).
6. Baseline spirometry
7. Lavage with normal saline to both nares to clear secretions and prepare for placement of allergen.
8. Total nasal symptom score (TNSS)
9. Peak nasal inspiratory flow (PNIF) measurement
10. Graded nasal allergen challenge using both nares with TNSS after each dose.  
Nasal allergen challenge will be provided in a graded dose fashion 0 AU, 100 AU, 500 AU and then 1,000 AU separated by 10 minutes. Dilutions will be provided by the University of North Carolina Hospitals Investigational Drug Service. Over 10 minutes, symptoms will be monitored and scored. Increasing concentrations of dust mite allergen dilution are deposited into the nose until the TNSS reaches a total of 8 or more (described below) and PNIF is reduced by at least 50%. An oral exam will occur prior to each dose. The cumulative allergen dose producing a TNSS of  $\geq 8$  and reduction in PNIF of  $\geq 50\%$  will be considered the provocative dose of allergen. Failure to achieve TNSS of  $\geq 8$  and reduction in PNIF of  $\geq 50\%$  will result in screen failure.
11. Subjects will be monitored for 90 minutes from the last dose of nasal allergen. Oral and upper airway exam, vital signs and spirometry will be performed at 30 and 60, and a physical exam at 90 minutes. At 90 minutes, if no significant findings on exam and no significant reduction in FEV1 (<10% reduction from baseline), the subject will be discharged.

#### **Post Nasal Allergen Challenge Telephone Follow up (24 hours after Visit 0)**

Subjects will be contacted for phone call follow-up 24 hours after allergen challenge (see phone script included in the study worksheets section)

#### **Visit 1: Baseline visit (at least 7 days but within 2 months of screening)**

1. Review of medical history including present medications
2. Obtain diaries detailing number of e-cig uses or number of cigarettes smoked per day (e-cig users and cigarette smokers only)
3. Urine pregnancy test for females of child bearing potential.
4. Nasal epithelial cell sampling of the right nare for mRNA to evaluate TLR2, TLR3, TLR4, TLR7, NLRP3, NLRP12, and CD14 expression)
5. Discharge to home.

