***Nasal Epithelial Biopsy:***

This is a non-invasive biopsy procedure performed to retrieve a small cluster of cells from each of the nasal cavities. For the nasal biopsy procedure, the subject will be seated comfortably in a straight-backed chair or reclining on an examination table with the head tilted as far back as possible while remaining comfortable. Subjects will be given no medication, sedation, or anesthesia for this procedure. A short, sterile plastic sampling device called a curette will be inserted into one of the nasal cavities and the surface of the nasal cavity will be stroked several times for approximately 5 seconds in order to obtain a small cluster of cells. Due to the potential for the biopsy itself to create a local inflammatory response, we will ensure that visit 2 occurs no sooner than 14 days after visit 1 to allow for dissipation of this inflammatory response before collection of nasal fluid samples. We will sample nasal epithelium from the right nare during visit 1 and from the left nare during visit 2 to ensure we obtain adequate epithelial samples on each occasion.

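### Nasal epithelial gene expression (exploratory): the fixed right-then-left nare order makes a within-group before/after change inseparable from a left-right difference, and 7 days after the screening challenge is not justified for the baseline sample

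*Combined protocol and SAP*

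**What the plan says.** Section c (Design of Study) includes mRNA from nasal epithelial cells among the secondary and exploratory endpoints, "to examine gene expression profiles before and after nasal allergen challenge". The Exploratory Endpoints section lists the epithelial targets: TLR2, TLR3, TLR4, TLR7, NLRP3, NLRP12 and CD14.

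The sampling rules are these:

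- **Visit 0 (screening):** "Graded nasal allergen challenge using both nares with TNSS after each dose". A subject who does not reach a TNSS of at least 8 with a PNIF fall of at least 50% is a screen failure, so everyone sampled later has reacted to allergen in this study.
- **Visit 1:** "Baseline visit (at least 7 days but within 2 months of screening". The only pre-challenge epithelial sample is taken here, from the right nare.
- **Visit 2:** at least 14 days after Visit 1. The post-challenge epithelial sample is taken from the left nare, 4 hours after allergen.
- **Nasal Epithelial Biopsy:** "We will sample nasal epithelium from the right nare during visit 1 and from the left nare during visit 2". The reason given is to obtain adequate samples on both occasions.

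The infection rules refer to challenge. Exclusion 14 reads: "Viral upper respiratory tract infection or other acute inflammatory conditions of the nose or paranasal sinuses, such as sinusitis, within 4 weeks of challenge". Exclusion 15, and the deferral rule under Measures to minimize risk, are tied to challenge in the same way. The Visit 1 list has a history and medication review but no nasal examination and no TNSS.

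The Analysis Plan covers nasal eosinophils and ECP only. It gives no method for epithelial mRNA and no adjustment for side or for the interval between visits.

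**The concern.** A before/after change is informative about allergen only if the two samples differ in little besides allergen. Here they also differ in side, in the same direction in every subject. The adequacy reason explains why the second sample comes from the other nare. It does not explain why all subjects start on the right.

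The baseline sample is also not clearly unchallenged. The nare sampled at Visit 1 received allergen at Visit 0, possibly only a week earlier, and nothing in the Visit 1 procedures defers the sample for a respiratory infection. A baseline still shifted by either would distort the measured change, and a baseline still raised would shrink it. If the groups recover at different rates or return after different intervals, the distortion would differ by group.

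At stake is the interpretation of one exploratory endpoint. It is, however, the endpoint for which each subject undergoes two curette samplings, and the only research specimen collected at Visit 1.

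**Working it through.** The documents give no sample size, power or effect figure for this endpoint, so there is no stated figure to reproduce.

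**Inputs.** 15 subjects per group (section b); right nare at Visit 1 and left nare at Visit 2 (section e; Nasal Epithelial Biopsy); minimum intervals of 7 days (Visit 0 to 1) and 14 days (Visit 1 to 2); criterion p ≤ 0.05 (Analysis Plan).

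**1. Timing.** Visit 0 to Visit 1: at least 7 days. Visit 0 to Visit 2: at least 7 + 14 = 21 days. The 7-day minimum applies only to the epithelial baseline. Nasal lavage, ELF and blood baselines are all taken at Visit 2 before the challenge.

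**2. What the change measures.** Let C be the challenge effect, S the left-minus-right difference, and K the residual effect of the Visit 0 challenge at Visit 1. Then

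observed change (left, after − right, before) = C + S − K.

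**3. Can C and S be separated now?** Model one group with 15 subject effects, a post-challenge indicator and a left-side indicator: 17 columns. Every before sample has (post, left) = (0, 0) and every after sample has (1, 1). The last two columns are identical and the rank is 16 of 17. C and S are completely aliased.

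**4. With the order alternated, 8 right-first and 7 left-first.** Right-first subjects have change C + S − K; left-first subjects have C − S − K. Half the sum of the two means estimates C − K, and half the difference estimates S. The rank is 17 of 17. With residual variance σ² per sample:

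- Var(challenge estimate) = ¼ × 2σ² × (1/8 + 1/7) = 0.1339σ².
- Without a side term: 2σ²/15 = 0.1333σ².
- Ratio = 1.0045, or about 0.4% more variance. One residual degree of freedom is also lost (15 − 1 = 14 becomes 15 − 2 = 13).

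K stays in the estimate, so changing the side order does nothing about carry-over.

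**5. Between groups.** For groups 1 and 2 the difference in changes is (C₁ − C₂) + (S₁ − S₂) − (K₁ − K₂). A common S cancels. K cancels only if residual response and Visit 0 to Visit 1 interval are similar across groups.

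**6. Illustration under assumed bias.** The documents give no value for S or K. Suppose C = 0 and the net bias S − K is b standard deviations of the within-subject change. A two-sided 0.05 paired t test with n = 15 (14 df, noncentrality b√15) rejects with probability:

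| Assumed b | Noncentrality | Rejection probability |
|---|---|---|
| 0.25 | 0.97 | 14.7% |
| 0.50 | 1.94 | 43.8% |
| 0.75 | 2.90 | 77.1% |

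The nominal rate is 5%. Both the bias and the test are assumptions, since the Analysis Plan names no test for this endpoint. The table shows sensitivity only.

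**The case against.** The best defence is that the study compares groups, and a side difference shared by all groups drops out of that comparison. This stands, and it confines the side problem to within-group change unless the left-right difference itself varies by group. The endpoint is also exploratory in a pilot, and switching nares has a stated reason. Both points limit the importance of the problem, but neither supports one fixed order.

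On carry-over, the defence is that none has been shown. Section f reports that nasal symptoms in the laboratory's previous challenges typically resolved within 24 to 48 hours; 7 days is 3.5 times the upper figure and is only the minimum of a window that runs to 2 months. This stands as far as symptoms go. It is silent on mucosal gene expression, so the interval is unjustified but not shown to be too short.

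Four stronger readings may tempt a reader, and the documents do not support them:

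- **That the protocol breaks its own 14-day standard.** The biopsy section says "we will ensure that visit 2 occurs no sooner than 14 days after visit 1 to allow for dissipation of this inflammatory response", which concerns inflammation from the curette. Exclusion 16, "Participating in an allergen inhalation study within 2 weeks of this challenge", spaces another study from the challenge, and the Visit 0 to Visit 2 gap of at least 21 days exceeds it. Neither sets an allergen wash-out before Visit 1.
- **That a subject with a cold at Visit 1 could be challenged exactly 4 weeks later.** Measures to minimize risk counts the 4 weeks from complete resolution, so that subject would be deferred. The narrower gap remains: Visit 2 has no maximum interval from Visit 1, so it can be postponed while a baseline taken during the cold stands.
- **That nasal medication is uncontrolled at Visit 1.** Inclusion 4 already requires antihistamines to be withheld for a week before the baseline visit, and exclusion 4 bars nasal steroids, cromolyn (apart from pre-exercise use) and leukotriene antagonists in the past month.
- **That gene expression before and after challenge cannot be studied at all.** Blood mRNA is drawn before and 4 hours after challenge on the same day, and between-group comparison of epithelial changes remains possible.

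**Conclusion.** The point holds for one exploratory endpoint. Its two parts differ in certainty.

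- **Side.** The aliasing is certain by design and applies to every subject. The size of any left-right difference is unknown; the documents give no evidence for or against one. The consequence is that a within-group epithelial change cannot be attributed to allergen.
- **Baseline condition.** Carry-over from Visit 0, or a recent respiratory infection at Visit 1, is permitted by the rules. It is not demonstrated, and its size is unknown.

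The primary endpoint, ECP and blood mRNA are untouched. Between-group comparison of epithelial changes is protected from side if the side effect is common to the groups, and from carry-over only if residual response and interval are similar across groups. I rate this as minor to moderate. It is worth correcting because the main correction costs almost nothing.

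**What to change.** **Main change.** Within each group, randomise or alternate the first-sampled nare so that about half the subjects go right then left and half left then right. Use the other nare at Visit 2, which keeps the adequacy rationale. Add to the Analysis Plan a short statement of how epithelial expression will be analysed, with side in the model. The cost is an allocation list, a line of protocol text, about 0.4% more variance for the challenge effect and one degree of freedom per group. No procedure is added.

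**Secondary change.** Record the Visit 0 to Visit 1 interval and, at the Visit 1 history review, any recent respiratory infection. Report a sensitivity analysis of the epithelial change on both. Alternatively, state why 7 days suffices for this sample, or lengthen that minimum. Recording costs two data items; lengthening would delay some Visit 1 appointments. This part is needed separately, because balancing side does not remove carry-over or any other difference between the two visits.

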#### **Visit 2: Nasal Allergen Challenge visit (to occur at least 14 days after Visit 1)**

1. Review of medical history including present medications
2. Obtain diaries detailing number of e-cig uses or number of cigarettes smoked per day (e-cig users and cigarette smokers only)
3. Urine pregnancy test for females of child bearing potential, and urine for NNAL and cotinine.

4. Physical examination (PE to include vital signs, assessment of the head, neck, chest, and baseline oral exam including the uvula by study MD)
5. Baseline TNSS and PNIF
6. Spirometry
7. Epithelial lining fluid (ELF) collection from both nares to measure baseline cytokines (ECP, Leukotrienes C4, D4, and E4; Prostaglandin D2, GM-CSF, IL-4, IL-8, IL-13, RANTES, Eotaxin, soluble CD14 (LPS-binding protein), TNF, IL1, IL6, CCL2 (MCP-1), CCL3 (MIP-1 $\alpha$ ), CCL4 (MIP-1 $\beta$ ))
8. Nasal lavage of both nares for baseline assessment of nasal fluid cellularity
9. Venipuncture for evaluation of baseline complete blood count and differential, Der f IgE levels, mRNA, cytokines, and flow cytometry for the following cell surface markers: CD11b, CD14, CD80/86, HLA-DR, TLR 4, Fc $\epsilon$ R1.
10. Nasal allergen challenge with the previously demonstrated provocative dose of allergen administered with equal distribution between the nares. An oral exam will occur prior to administration of allergen.
11. Post nasal challenge TNSS and PNIF measurements performed at 10, 30, and 60 minutes then hourly for 4 hours.
12. Post nasal challenge, vital signs, spirometry and oral and upper airway exam will be performed at 30, 60, and 90 minutes following allergen challenge. At 4 hours a physical exam will be performed along with vital signs and spirometry.
13. Nasal lavage, nasal epithelial cell sampling (from the left nare), ELF collection, and venipuncture will occur 4 hours after allergen challenge for measurements as noted above.
14. If any reduction in FEV1 $\geq$ 10% from baseline is seen during the initial 90 minutes post-allergen challenge, spirometry will be repeated prior to discharge. If spirometry is not significantly reduced (reduction of <10% from baseline), the subject will be discharged.

